We recently found that ATP-dependent, apical Cl⁻ secretion and ASL fluid regulation depend on the activation of apically expressed large conductance, Ca²⁺ activated and voltage-dependent potassium (BK) channels. By secreting K⁺, apical BK channels provide a driving force for apical Cl⁻ secretion via Cl⁻ channels, forming a so-called apical loop current. This BK function is critically important since inhibition of BK channels reduces ASL volume significantly (in the presence or absence of functional CFTR), thus shifting the focus of ASL volume regulation upstream from Cl⁻ channels to BK channels.

Increased airway TGF-ß1 expression and signaling is common in active cigarette smokers and ex-smokers with COPD. Our preliminary data show that TGF-ß1 and cigarette smoke exposure decrease BK activity and cause ASL volume depletion. We therefore propose that smoke exposure, via TGF-ß1 production, leads to apical BK channel dysfunction to cause ASL volume depletion and mucociliary dysfunction in smokers and ex-smokers with COPD. BK rescue is associated with increased ASL volume and CBF. Therefore, restoring ASL volume requires BK channel rescue or inhibition of TGF-ß signaling. Clinically used Angiotensin II Receptor Blockers (ARBs) are known to inhibit TGF-ß signaling and present a "low-hanging-fruit" approach (medication already in clinical use) for intervention in COPD. In a murine model, losartan has previously been shown to attenuate cigarette smoke-induced lung injury and to rescue lung architecture. Our preliminary data suggest that losartan partially rescues BK channel function leading to increased ASL volume and CBF in airway epithelial cells exposed to smoke. The long-term goal of this study is therefore to evaluate the effect of currently available and clinically useful TGF-ß1 signaling inhibitors on mucociliary function in individuals with smoke-associated airway diseases, such as chronic bronchitis and COPD.

This is a proof of concept, open label protocol to evaluate the effect of ARB on cigarette smoke-induced lung injury in smokers, ex-smokers with and without COPD, giving 50 mg and subsequently 100 mg losartan for 4 weeks

Study Population

Group I, COPD:

10 ex-smokers not treated with ARBs **with** evidence of fixed airflow obstruction by pulmonary function testing (PFT), decreased DLco **and** with the clinical diagnosis of chronic bronchitis.

Group II, non-COPD:

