20 active smokers not treated with ARBs **without** evidence of airflow obstruction by PFT and **normal** DLco but **with** the clinical diagnosis of chronic bronchitis.

Group III, lung healthy, life-time non-smoker:

20 never smokers not treated with ARBs **without** evidence of airflow obstruction by PFT, a **normal** DLco **and no** evidence of the clinical diagnosis of chronic bronchitis

Groups will be appropriately balanced considering COPD stage, smoking status, lung function and age.

Inclusion and Exclusion Criteria

Inclusion criteria

- Age between 35 and 75 years old
- ex-smokers (>10 pack-years of cigarette smoking) not treated with ARBs and with evidence of fixed airflow obstruction by pulmonary function testing (PFT), decreased DLco and with the clinical diagnosis of chronic bronchitis. Or

active smokers (>10 pack-years of cigarette smoking) not treated with ARBs **without** evidence of airflow obstruction by PFT and **normal** DLco but **with** the clinical diagnosis of chronic bronchitis.

Or

never smokers not treated with ARBs **without** evidence of airflow obstruction by PFT, a **normal** DLco **and no** evidence of the clinical diagnosis of chronic bronchitis

• Ability to understand and willingness to sign consent documents

Exclusion criteria:

- Current therapy with ACE inhibitor, intolerance to ARB
- Women of child bearing potential
- Regular use of NSAIDs or potassium supplementation, treatment with aliskiren, anticoagulation
- COPD exacerbation requiring treatment within 6 weeks
- Oral corticosteroid use within 6 weeks
- Significant hypoxemia (oxygen saturation <90% on room air), chronic respiratory failure by history (pCO₂ > 45 mmHg) and forced expiratory volume in 1 second (FEV₁) below 40%, clinical evidence of cor pulmonale

- Untreated arterial hypertension (systolic blood pressure >140 mm Hg, diastolic blood pressure > 90 mm Hg)
- Blood pressure less than 100 mm Hg systolic or 70 mm Hg diastolic at Screening visit and Visit 2.
- Cardiac, renal, hepatic (LFTs > 3x normal upper limit), neurological, psychiatric, endocrine or neoplastic diseases that are judged to interfere with participation in study
- History of renal artery stenosis
- Concomitant airway disorders other than COPD and chronic bronchitis, such as bronchiectasis and asthma (history and reversible airflow obstruction by ATS criteria)
- History of pulmonary malignancies, and any other malignancies in the last 5 years
- History of thoracic surgery.

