NPD measurement will be performed according to standard procedures. In this aim, we will use one side of the nose for the evaluation of the function of CFTR and CaCC by measuring the potential differences by initial blocking ENaC with amiloride, then using chloride free solution and isoproterenol to evaluate CFTR function, followed by ATP to evaluate CaCC function. In the other nostril, the same experiment will be repeated as mentioned above, except that after blocking ENaC with amiloride and perfusion with chloride-free solution the CFTR will not be stimulated with isoproterenol, but ATP will be used to maximize the CaCC signal. We will adjust the way of measuring the NPD for aim 2.2 depending of the results in aim 2.1.

TGF-ß and citokines will be measured using Leukosorb, a noninvasive sampling method of the nasal mucosa as previously reported. In addition, we will obtain a small amount of nasal epithelial cells to measure TGF-ß by qPCR.

Study Visits:

V1 (Screening Visit): This will be a single visit for the purpose of determining eligibility, obtaining informed consent, and recording the necessary data will include:

- Assessment of general health status and physical examination (incl. vital signs)
- Urine pregnancy test if indicated (female, child bearing age)
- Spirometry pre- and post-bronchodilators, DL_{co}, lung volumes
- Pulse oximetry
- Review of laboratory values, or if not available: venous blood sampling to assess for renal and liver abnormalities (then the measurements will be done within a week in an additional visit), CRP
- If inclusion criteria fulfilled and no exclusion criteria found:
 - Enrollment

- Completion of respiratory questionnaires (COPD only)
- Six minute walk test (COPD only)
- BODE index calculation

V2 (week 4): This visit (and the two following ones) will only done for the groups not treated with any ARBs. This visit will occur 4 weeks (\pm 4 days) after V1.

- We will again review laboratory values (CMP, CRP), repeat urine pregnancy test if indicated (female, child bearing age).
- The following procedures will be executed:
 - Completion of respiratory questionnaires (COPD only)
 - Six minute walk test (COPD only)
 - BODE index calculation
 - NPD measurement followed by nasal fluid recovered by Leukosorb filter paper and nasal cell collection for TGF-ß

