COPD is more common among men than women, although the prevalence is increasing in women. COPD is rare among African-Americans. Less information is available about Hispanics, which are a heterogeneous group. The planned accrual of minority groups reflects the prevalence of COPD in our region in South Florida.

Setting

The Human Research Laboratory, Division of Pulmonary, Allergy, Critical Care and Sleep Medicine, is located on the 6th floor of the Doctor's Office West Building at the University of Miami on the Medical School Campus. It has 2,200 square feet of space for evaluation of patients for pulmonary research. This space is equipped with spirometers, a nSpire[®] HDpft plethysmograph including DLco measurement, , blood pressure machines, pulseoximeters, 12-lead ECG machine, ACLS equipment and setup for 6-minute walk tests, including O₂ tanks, an HP 78352A monitor for heart rate and ECG monitoring (3 lead ECG cables). Other equipment includes a DeVilbiss nebulizer, Ultrasonic nebulizer and - 20°C freezer.

We have the ability to draw blood, prepare specimens for laboratory analysis. Our staff is BLS, GCP, OSHA and IATA certified and follows UN 1845 and 3373 regulation for the guidelines of shipping biological materials. Physicians are BLS and ACLS certified. We have a fully functional nasal potential difference (NPD) measurement unit (use certified by Cystic Fibrosis Foundation Therapeutic Development Network: CFF TDN). [name] has an office within this setting.

Recruitment Methods

Forty subjects will be enrolled from two outpatient clinics run by members of the Division of Pulmonary, Allergy, Critical Care and Sleep Medicine, Department of Medicine, at the University of Miami Miller School of Medicine considering 20% of screening failure to enroll 30 patients on the treatment phases. Collectively, ~400 patients with COPD are seen at the two sites annually. Smokers without COPD and lung-healthy lifetime non-smokers will be recruited from the pre-operative clinics at the University of Miami Hospitals and Clinics.

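### Planned group sizes (50), enrolment (forty) and number treated (30) do not agree as written, and the visit schedule read literally doses 50, including 20 never-smokers

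*Combined protocol and SAP*

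**What the plan says.** **Group sizes.** Study Population defines Group I as "10 ex-smokers not treated with ARBs", Group II as "20 active smokers not treated with ARBs" and Group III as "20 never smokers not treated with ARBs".

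**Recruitment.** Recruitment Methods states that "Forty subjects will be enrolled from two outpatient clinics" of the pulmonary division, "considering 20% of screening failure to enroll 30 patients on the treatment phases". The same paragraph then says that "Smokers without COPD and lung-healthy lifetime non-smokers will be recruited from the pre-operative clinics", which covers Groups II and III.

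**Point of enrolment.** In Study Visits, V1 lists enrolment under the condition "If inclusion criteria fulfilled and no exclusion criteria found".

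**Who goes on to treatment.** V2, at which the first losartan supply is dispensed, is introduced as a visit that, with the two after it, "will only done for the groups not treated with any ARBs". The dispensing line refers to subjects generally. Appendix I puts Visits 2 to 6 under a heading for subjects not on ARBs. Treatment arms speaks only of patients and exempts no group. The design sentence that closes Background describes the drug's effect in smokers and ex-smokers and does not mention never-smokers.

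**The concern.** A reader who adds up the groups gets 50. A reader of Recruitment Methods gets forty enrolled and 30 treated. A site that follows the visit schedule would dose every ARB-free subject, and all three groups are defined as ARB-free. No sentence expressly includes Group III in the treatment phase or excludes it.

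Two things depend on the answer:

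- **Number exposed to drug: 30 or 50.** The difference consists entirely of healthy never-smokers. The protocol states no direct benefit to participants and sets up no formal safety board, so this count should not have to be inferred.
- **The analysis.** Statistical analysis plans a regression on groups and doses. Group III either contributes observations at each dose or serves only as an untreated reference. These are different models.

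**Working it through.** **Inputs.** Group sizes 10, 20 and 20 (Study Population). Forty enrolled, 20% screening failure and 30 on treatment (Recruitment Methods).

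**1. The plan's own step.** Number to screen = target / (1 − failure rate) = 30 / 0.80 = 37.5, so 38. Forty is close to this, with a margin of 2. In the other direction, 40 × 0.80 = 32. Going from forty to exactly 30 implies a failure rate of 1 − 30/40 = 25%. The step is acceptable as a rounded allowance.

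**2. Totals.** 10 + 20 + 20 = 50. Groups I + II: 10 + 20 = 30, which matches the stated treated number.

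**3. Shortfall against 50, by reading of the forty.**

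| Reading | Subjects obtained | Shortfall |
|---|---|---|
| Forty screened for Groups I + II; Group III additional | 30 + 20 = 50 | 0 |
| Forty enrolled after eligibility is confirmed, all groups | 40 | 50 − 40 = 10 |
| Forty screened for all groups, 20% fail | 40 × 0.80 = 32 | 50 − 32 = 18 |
| The stated 30 taken as the yield for all groups | 30 | 50 − 30 = 20 |

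**4. Does the text support the zero-shortfall reading?** Three places conflict with it.

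- *Clinics.* The forty are tied to two pulmonary outpatient clinics, but Group II comes from the pre-operative clinics. Taken literally, the forty would all be COPD patients, for a Group I of 10.
- *Enrolment.* V1 enrols only after eligibility is confirmed, so screening failures are not enrolled subjects. Recruitment Methods nevertheless uses the same verb for the forty, before failures, and for the 30, after them.
- *Treatment.* The V2 rule and the Appendix I heading cover ARB-free subjects. All three groups meet that condition by definition, so the rule removes nobody.

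**5. Number exposed.** As stated: 30. By the visit schedule: 50. Difference: 20, and 20/30 = 67%.

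**6. Screening total for 50.** The 20% rate is given only in connection with the 30 on treatment, so applying it to Group III is an assumption. Groups I and II: 10/0.8 = 12.5 (13) and 20/0.8 = 25, together 38. Group III at 20%: 20/0.8 = 25, giving 38 + 25 = 63. With no failures in Group III the total is 38 + 20 = 58. If forty are screened for Groups I + II and 25 for Group III, it is 65. Replacement of withdrawn subjects (Removal of Subjects from Study) would add to any of these.

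**The case against.** The best defence is that nothing fails to add up. The phrase about treatment phases limits the 30 to a treated subset, 30 is exactly Groups I + II, and the design sentence concerns smoke-induced injury, which never-smokers do not have. The ARB-free condition separates none of the defined groups, so it is weak evidence of an intention to dose Group III. On this view the clinic sources and the use of the word enrolled are loose drafting.

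Much of this stands. It may well be what was meant, and it rules out several stronger inferences that a reader might draw:

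- *That forty-to-30 is a calculation error.* It is not: 38 is needed and forty is given.
- *That the trial will fall short by a known number.* The shortfall depends on the reading and may be zero.
- *That the protocol intends to treat never-smokers.* The schedule reaches them only because no group is exempted, and Treatment arms contains no ARB-free condition.
- *That no total or treated number can be found.* Group sizes adding to 50 and a treated number of 30 are both given. The difficulty is that other passages contradict them.
- *That the objective limits treatment to the 10 subjects of Group I.* It names smokers as well as ex-smokers with COPD, whereas Group I has ex-smokers only, so that count is strained.

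The defence does not remove the conflict. Its reading appears nowhere in the text, and staff work from the visit schedule, which has no step that keeps Group III from receiving drug.

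**Conclusion.** Wrong as written: an internal inconsistency in a stated sample size and a stated treated number. The figures are compatible only on an unstated reading that conflicts with three parts of the protocol. Followed literally, the schedule exposes 50 subjects against the stated 30.

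The consequence is limited. Each subject in Groups I and II serves as his or her own control, so the within-person losartan effect there does not change. No power calculation is given, so none is disturbed. What remains open is the exposed number (30 or 50) and whether Group III is a treated comparator or an untreated reference in the between-group and dose regression.

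The 50, the 30 and the difference of 20 need no assumption beyond reading the visit rules literally. The screening total of about 63 rests on the assumed Group III failure rate.

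**What to change.** 1. Replace the recruitment sentence with a table giving, for each group, the numbers screened, enrolled and treated and the source clinic, in agreement with Study Population. Use enrolled in one sense throughout, consistent with V1.
2. Restate the screening total for all 50. If 20% failure is assumed for Group III as well, this is about 63 (13 + 25 + 25), before replacement of withdrawals. State the rate used for each group.
3. Reconcile the design sentence, Treatment arms, the V2 rule and dispensing text, Recruitment Methods and Appendix I on whether Group III enters the treatment phase. This review does not say which is right.
4. If Group III is untreated, name the visit at which its nasal potential difference (NPD) is measured. Study Procedures lists NPD for all subjects, but neither the V1 list nor Appendix I places it at V1, and at V2 it comes with dispensing. Footnote g of Appendix I allows V1 and V2 to be combined but does not separate the two. Label Group III an untreated reference in Statistical analysis.
5. If Group III is treated, correct the treated number from 30 to 50.

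The cost is protocol wording and a restated screening figure. No enrolment is needed beyond the 50 already planned, apart from replacements that the protocol already allows.

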Appendix I

	For all	For subjects who are not on ARBs treatment				
	subjects					
	Visit 1 Screening	Visit 2 ^g 4 weeks (± 4 days) after V1	Visit 3 Phone Call 1 weeks (± 4 days) after V2	Visit 4 8 weeks (± 4 days) after V2	Visit 5- Phone Call 9 weeks (± 4 days) after V2	Visit 6 12 weeks (± 4 days) after V2
Informed Consent	X					
Assessment of health status	X	Х		Х		Х
Medical History	Х					
Occupational history	Х					
Smoking History	Х					
Concomitant medication	X		Х		Х	
Urine cotinine test	Х	Х		Х		X
AE and SAE		Х	Х	Х	Х	X
Physical exam	Х	Х		Х		Х
Vital signs	X	X		Х		Х
Urine pregnancy test ^a	Х	Х		Х		Х
β–HGC ^b	Х	X		Х		X
Complete Pulmonary function test pre and post	X					
Renal and liver blood test ^c	X	X		Х		X
CRP ^d	Х	Х		Х		X
Respiratory Questionnaires ^e	X	X		Х		X
6 Minute Walk Test ^f	Х	Х		Х		X
NPD measurement		Х		Х		Х
Nasal fluid for TGF -β measurement	X	Х		Х		Х
Drug Dispensation (losartan 50 mg or 100 mg)		Х		Х		
Drug Compliance				Х		Х

a- Only for female

b- If urine pregnancy test is positive

c- Only if results are not available on the last 6 month

d- Only if results are not available on the last 6 month

e- Respiratory Questionnaire (BCSS, MRC, Charlson co-morbidity index, SGRQ, CAT) will be performed at each visit before any study procedure (COPD group only)

f- 6MWT will be performed for participants on the COPD group only

g- Visit 1 and 2 could be combined if the subject is not on ARBs treatment and has renal and liver blood test results available on the last 6 month.

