 - Subjects will be provided with a 4-week supply of 50 mg losartan for daily use (first dose given in clinic; observation with blood pressure monitoring for 2 hours).

V3 (week 5 ± 4 days):

Telephone visit to follow up on symptoms and tolerability of medication.

V4 (week 8 ± 4 days):

- The following procedures will be executed:
 - Monitor for adverse events.
 - Completion of respiratory questionnaires (COPD only)
 - Six minute walk test (COPD only)
 - Venous blood sampling to assess for renal and liver abnormalities and CMP, CRP
 - Urine pregnancy test (if applicable)
 - BODE index calculation
 - Nasal fluid recovered by Leukosorb filter paper and nasal cell collection for TGF-ß
 - Subjects will be provided with a 4-week supply of 50 mg losartan for twice daily use (100 mg)

V5 (week 9 ± 4 days):

Telephone visit to follow up on symptoms and tolerability of medication.

V6 (week 12 ± 4 days) or Early Termination Visit:

- We will draw laboratory (CMP, CRP). Repeat pregnancy test if indicated (female, child bearing age).
- The following procedures will be executed:
 - Monitor for adverse events.
 - Completion of respiratory questionnaires(COPD only)
 - Venous blood sampling to assess for renal and liver abnormalities and CMP, CRP
 - Urine pregnancy test (if applicable)
 - Six minute walk test (COPD only)

- BODE index calculation
- NPD measurement followed by nasal fluid recovered by Leukosorb filter paper and nasal cell collection for TGF-ß

Unscheduled visit (up to 2 visits) will apply if there is a need to repeat study procedures.

Subjects are allowed to be re-screened one time as per PI discretion.

Specimen Banking

Not applicable.

Data Management

Data collected will include demographics, clinical symptoms, health-related quality of life, and pulmonary function test data. Samples to be collected include NPD measurement followed by nasal fluid and cell collection for TGF-ß. We will obtain blood for safety reasons (liver and renal function) and for evaluation of an inflammatory marker. No personal identifiers will be collected and each patient's data will be coded.

Safety Reporting

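### Appendix I places V4, V5 and V6 at 8, 9 and 12 weeks after V2, where the rest of the protocol implies 4, 5 and 8; followed literally, the 50 mg assessment falls 24 to 32 days after the supply ends

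*Combined protocol and SAP*

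**What the plan says.** Appendix I gives the post-dose visits relative to V2. The first tolerability call is headed "Visit 3 Phone Call 1 weeks (± 4 days) after V2". The 50 mg assessment carries the header "Visit 4 8 weeks (± 4 days) after V2", while the second call is shown as "Visit 5- Phone Call 9 weeks (± 4 days) after V2" and the 100 mg assessment as "Visit 6 12 weeks (± 4 days) after V2".

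The Study Visits section labels visits by week number. For V2, labelled week 4, it says "This visit will occur 4 weeks", counted from V1, with a window of 4 days either side. V3 is headed "V3 (week 5 ± 4 days" and V4, V5 and V6 are at weeks 8, 9 and 12, each with the same window. A 4-week supply of 50 mg once daily is handed out at V2, with the first dose taken in clinic. A 4-week supply of 50 mg twice daily is handed out at V4.

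The Treatment arms section sets four weeks at each dose, with re-evaluation when each period ends. The Objectives call for NPD to be repeated during treatment at each dose.

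Footnote g to Appendix I adds an option: "Visit 1 and 2 could be combined if the subject is not on ARBs treatment", provided recent renal and liver results are available.

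**The concern.** The two schedules cannot both be right. The text and the table agree for V3, but the table is four weeks later for V4, V5 and V6. The table's 8, 9 and 12 are exactly the text's week numbers from V1, so the likely cause is a wrong anchor.

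What is at stake is the 50 mg measurement. Each subject is his or her own control and doses are compared by regression, so the V4 value enters the dose comparison directly. If V4 is held when the table says, that value describes a subject who has been off drug for about four weeks. Under the table, the V4 measures affected are NPD, nasal TGF-ß and, in the COPD group, the questionnaires and the 6-minute walk.

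Staff cannot simply set the table aside. It is the only visit-level listing that puts NPD at V4.

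The text also needs care. When V1 and V2 are combined, week 8 counted literally from V1 is 8 weeks after the first dose, and the V3 tolerability call comes after the tablets have run out.

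**Working it through.** **Inputs.** Study Visits: V2, V3, V4, V5 and V6 at weeks 4, 5, 8, 9 and 12, with V2 defined from V1; windows of ± 4 days; 4-week supplies at V2 and V4. Appendix I: V3, V4, V5 and V6 at 1, 8, 9 and 12 weeks after V2, ± 4 days.

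**Step 1. Put both schedules on the same anchor.** With V1 and V2 separate, weeks after V2 = text week − 4.

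| Visit | Text, weeks from V1 | Text, weeks after V2 | Appendix I, weeks after V2 | Difference |
|---|---|---|---|---|
| V3 | 5 | 1 | 1 | 0 |
| V4 | 8 | 4 | 8 | 4 |
| V5 | 9 | 5 | 9 | 4 |
| V6 | 12 | 8 | 12 | 4 |

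The table's figures for V4 to V6 are reproduced only by counting from V1. Counted from V2, as labelled, they do not follow from the text or the supplies.

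**Step 2. Time off drug at V4 under Appendix I.** Supply = 4 × 7 = 28 days. V4 = day 56 ± 4, so day 52 to 60 after V2.

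- Days past the supply: 52 − 28 = 24; 56 − 28 = 28; 60 − 28 = 32.
- Share of the V2 to V4 interval: 24/52 = 46%; 28/56 = 50%; 32/60 = 53%.
- If the clinic dose comes out of the supply and the last tablet is taken on day 27, the time since the last dose is 25 to 33 days.

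**Step 3. The text, V1 and V2 separate, both windows counted from V1.** V2 is on day 24 to 32 and V4 on day 52 to 60. The V2 to V4 interval is 52 − 32 = 20 to 60 − 24 = 36 days, so at most 36 − 28 = 8 days are uncovered.

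**Step 4. The text, V1 and V2 combined, counted literally from V1.** V4 is on day 52 to 60 after the first dose, again 24 to 32 days past the supply. The V3 call is on day 35 ± 4 = 31 to 39, which is 3 to 11 days past day 28.

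**Step 5. The corrected schedule.** V4 is on day 28 ± 4 = 24 to 32 after V2, at most 32 − 28 = 4 days uncovered. V6 is on day 56 ± 4 = 52 to 60, so V4 to V6 is 52 − 32 = 20 to 60 − 24 = 36 days.

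**Step 6. The 100 mg assessment.** V4 to V6 is 28 days nominal, and 20 to 36 with both windows, under every schedule. V6 is therefore on drug at nominal dates and up to 36 − 28 = 8 days uncovered at the extreme.

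**Step 7. Study length, separate visits, V1 to V6.** Text: 12 weeks (84 days). Appendix I: 4 + 12 = 16 weeks (112 days).

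**The case against.** The strongest reply is that the intent is clear. The Objectives, the Treatment arms section, the visit text and the two supplies all point to four weeks per dose. A team that hands out a 4-week supply is unlikely to book the next dispensing visit eight weeks later, and nothing shows that the table was followed or takes precedence. This stands as a limit: the 24 to 32 days is conditional on the table being used. It does not remove the contradiction.

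On combined visits, only V2 is expressly tied to V1. The later headings carry bare week labels, and a sensible reader could keep V2 as the dosing anchor. That is fair. The figures in step 4 hold only under literal counting, which conflicts with the Treatment arms section. The ambiguity is still real and one phrase removes it.

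The remark in Safety Reporting that the study lasts about three months is weak evidence. It names no start point, and V2 to V6 under the table is also 12 weeks. The conclusion does not rely on it.

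The list of affected measures follows the table. CRP is left out because its footnote reads "d- Only if results are not available on the last 6 month", but the V4 text lists CRP without that condition and also lists BODE. Any CRP drawn at V4, and BODE through its walk and dyspnea components, would be affected too.

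Finally, the few uncovered days at the window extremes come from ordinary ± 4-day windows, not from the header error. That is correct, and it is why extra tablets are only optional.

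**Conclusion.** The Appendix I headers for V4, V5 and V6 are wrong as written. They should read 4, 5 and 8 weeks after V2. The slip is probably one of anchoring, and it should be fixed because the table is an operating schedule.

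If the table is followed, with no supply beyond the 4 weeks stated, the 50 mg assessment is made 24 to 32 days off drug, about half of the V2 to V4 interval. The effect on the results cannot be computed from the documents, because they do not say how fast any losartan effect fades. Dilution of the 50 mg effect could run from none to complete. The contrast of 100 mg with 50 mg would be distorted in a way that also depends on whether the undosed gap lowers the response at V6. The documents do not show which schedule was used.

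**What to change.** In Appendix I, change the headers to V4 = 4 weeks, V5 = 5 weeks and V6 = 8 weeks after V2, each ± 4 days. V3 stays at 1 week.

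In Study Visits, reword the headings for V3 to V6 to 1, 4, 5 and 8 weeks after V2, so that the schedule also holds when V1 and V2 are combined under footnote g. Correcting the table alone would leave that case open.

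The cost is three header cells and four visit headings, with no new visit or procedure.

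Optionally, dispense enough tablets to cover the windows: 4 extra days at V2 (4 × 1 = 4 tablets) and up to 8 extra days at V4 (8 × 2 = 16 tablets), at most 20 extra 50 mg tablets per subject.
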